All participants enrolled in the study, whether randomised or not, including those who withdrew prior to the randomisation.

Section 5: Trial Population

Screening data

Screening data has not been collected.

Eligibility

Trial inclusion and exclusion criteria are reported in the protocol [2]. Number of ineligible patients who were enrolled and randomised will be reported together with their reasons for ineligibility.

Recruitment

Recruitment will aim to obtain an equal proportion of people using MDI and IPT. CONSORT diagram will be presented (Figure 2).

[figure not shown]

Figure 2: Example of CONSORT diagram

Withdrawal/follow-up

Withdrawals will be reported as indicated in the CONSORT diagram above.

Timing of withdrawals for each category will be presented in a separate table (each cell will contain number of withdrawn participants):

Visit	Overall	IPT		MDI	
		Intervention arm	Standard arm	Intervention arm	Standard arm
V1					
V2					
V3					
V4					
V5					
V6					
V7					
V8					
V9					
V10					
V11					
V12					
V13					
V14					
V15					
V16					

Baseline participant characteristics

Participants' pre-randomisation characteristics will be presented in a table, separately for each arm of the study (control arm, intervention arm). Categorical characteristics will be presented as frequency (%) and continuous as median (IQR) [min, max] or mean (standard deviation) [min, max], depending on the distribution.

The following variables will be included:

- Age
- Sex (Male vs Female)
- Insulin delivery modality (MDI vs CSII)
- Study site
- Time in target range at randomisation (<= 55%, > 55%; and as continuous variable)
- Duration of diabetes (years)
- Pump duration (years) for CSII group only
- Weight (kg) at randomisation
- BMI (kg/m2) at randomisation
- HbA1c at enrolment (%, mmol/mol)
- HbA1c at randomisation (%, mmol/mol)
- C-peptide (fasting) at enrolment

- Total daily insulin (units) at enrolment
- Basal insulin proportion (%) at enrolment
- CHO-counting (yes vs no) at enrolment
- Gold score indicating hypoglycaemia awareness at randomisation
- Microvascular complications at enrolment
- Macrovascular complications at enrolment
- History of diabetic foot ulcer at enrolment
- Diabetic ketoacidosis in the year prior to enrolment
- Severe hypoglycaemic episodes in the year prior to enrolment

Formal statistical comparison of baseline characteristics between groups will not be performed, rather clinical importance of any imbalance will be noted.

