All secondary outcomes (except fasting capillary blood glucose and number of hypoglycaemic events) will be analysed using ANCOVA including treatment and baseline score of the outcome. Where the distribution of residuals is heteroscedastic even after logarithmic transformation, a Wilcoxon rank sum test will be performed (in which case no adjustments for baseline will be performed). With parametric methods, mean differences with 95% CI will be presented, whereas with non-parametric methods, median difference with 95% CI will be presented ([13]).

A mixed effects linear regression will be used to analyse fasting capillary blood glucose with random intercepts for individuals and study arm as a fixed effect.

The number of hypoglycaemic events will be analysed using Poisson regression or negative binomial regression if overdispersion is apparent.

Percent time in ranges, mean glucose, standard deviation and coefficient of variation will be performed separately for day (6:00 – 23:59) and night (0:00 – 5:59).

All analyses will be performed separately for mid-study and end-of-study data.

Sensitivity analysis

Due to exploratory nature of the outcomes, no sensitivity analysis will be performed.

Subgroup analysis

To estimate the effect of the intervention based on regimen (IPT or MDI), a treatment group by regimen interaction will be included in all models. Where non-parametric analysis will be performed, each regimen will be analysed separately.

2. Clinical outcomes

Outcome definition

- Change in average total daily dose of insulin and basal/bolus proportions taken over the last 7 days
- Change in insulin-to-carbohydrate ratio (ICR) (ICR is usually expressed in 1:X form where X represents grams of carbohydrates covered by 1 unit of insulin. This ratio can be constant throughout the day or can vary for breakfast, lunch and dinner times. It will be analysed separately for breakfast, lunch and dinner time, as well as a weighted average overall for the day)
- Change in body weight (kg)

All clinical outcomes are measured at randomisation, mid-study and end-of-study.

Analysis method

Linear regression will be used to evaluate the effect of treatment arm on the change score from baseline. Where the distribution of residuals is heteroscedastic even after logarithmic transformation, rank sum test will be performed.

All analysis will be performed separately for mid-study and end-of study.

Sensitivity analysis

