Due to exploratory nature of the outcomes, no sensitivity analysis will be performed.

Subgroup analysis

To estimate the effect of the intervention based on regimen (IPT or MDI), a treatment group by regimen interaction will be included in all models. Where non-parametric analysis will be performed, each regimen will be analysed separately.

3. Psychosocial, sleep and cognitive functioning

Outcome definition

- Psychological wellbeing
 - Hypoglycaemia Fear Survey II short form (HFSII-SF)
 - Behaviour subscale (0 to 20)
 - Worry subscale (0 to 24)
 - Hypoglycaemia Avoidance Scale (HAS) (currently being validated, therefore scales might change)
 - Behaviour subscale (0 to 48)
 - Worry subscale (0 to 48)
 - Problem areas in diabetes (PAID)
 - Total (0 to 100)
 - Diabetes positive wellbeing (W-BQ28)
 - Total (0 to 12)
- Quality of life
 - DAWN impact of diabetes profile (DIDP)
 - Total (1 to 7 for each dimension; and for total score)
- Treatment satisfaction
 - Diabetes treatment satisfaction questionnaire (DTSQs)

Total (0 to 36)

Diabetes treatment satisfaction questionnaire (DTSQc)

Total (- 18 to +18.)

- Sleep quality
 - Pittsburgh sleep quality index (PSQI)
 - Total (0 to 21)
 - Psychomotor Vigilance Test (averaged over visits 3-4, 9-10 and 12-13)
 - Average reaction time
 - Total number of lapses (response times above 500 milliseconds)
 - Average of the fastest 10% and slowest 10% of responses
 - o Karolinska Sleepiness Scale (averaged over visits 3-5, 9-11 and 12-14)
 - Average Score 1 to 9
 - Actigraphy and sleep diary (averaged over visits 3-5, 9-11 and 12-14)

- Average sleep time
- Average sleep efficiency (time asleep / total time in bed)
- Average sleep onset latency
- Memory
 - Prospective-retrospective memory questionnaire (PRMQ)
 - Total (16 to 80)

Analysis method

All outcomes will be analysed using ANCOVA including intervention group and baseline outcome score. Model residuals will be visually assessed to ensure assumptions are met and a logarithmic transformation of the outcomes will be performed in the presence of heteroscedasticity or non-normally distributed outcomes. A non-parametric analysis will be used if model assumptions are violated. The mean difference in outcomes with 95% confidence intervals will be presented for parametric analyses and the median difference in outcomes with 95% confidence intervals for non-parametric analyses.

Sensitivity analysis

No sensitivity analysis will be performed.

Subgroup analysis

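### The exploratory clinical outcomes are compared as change scores without the randomisation value as covariate, which gives up precision that the SAP keeps for most of its other continuous outcomes

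*SAP*

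**What the plan says.** SAP Section 6, Secondary outcomes, 2. Clinical outcomes, covers insulin ("Change in average total daily dose of insulin and basal/bolus proportions taken over the last 7 days"), the insulin-to-carbohydrate ratio and body weight, each defined as a change. A baseline value exists for all of them: "All clinical outcomes are measured at randomisation, mid-study and end-of-study". The model is then given as: "Linear regression will be used to evaluate the effect of treatment arm on the change score from baseline". The only further term is the treatment-by-regimen interaction in the subgroup paragraph. If residuals remain heteroscedastic after a logarithmic transformation, a rank sum test replaces the model.

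The neighbouring blocks differ. Under 1. Glucose control, the outcomes other than fasting capillary glucose and hypoglycaemic events "will be analysed using ANCOVA including treatment and baseline score of the outcome". Under 3. Psychosocial, sleep and cognitive functioning: "All outcomes will be analysed using ANCOVA including intervention group and baseline outcome score". The primary outcome also uses ANCOVA with baseline time in range, and its regimen interaction model includes that baseline value. The SAP gives no reason for treating the clinical outcomes differently.

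Section 4 labels all secondary outcomes exploratory and asks for 95% confidence intervals.

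**The concern.** Regressing the change on arm alone fixes the slope of follow-up on baseline at 1. ANCOVA estimates that slope from the data. When the true slope is below 1, subtracting the whole baseline value adds noise to the comparison, and the interval is wider than the collected data allow.

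The loss grows as the correlation falls. That is plausible for some of these outcomes. The SAP introduction says that the hybrid closed loop adjusts basal delivery automatically, and recruitment aims for equal numbers of injection and pump users. Basal share at randomisation may therefore predict follow-up basal share only weakly in the intervention arm. This is an inference from the design; the SAP gives no data on it.

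At stake is the precision of the arm comparisons at mid-study and end-of-study, and of the interaction models built on them. The primary analysis is not involved.

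A smaller point lies in the same paragraph. The SAP does not say what is to be logged. The logarithm of a zero or negative change is undefined, and changes in dose or weight will often be negative.

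**Working it through.** **The plan's own figures.** The SAP states no sample size, SD, correlation or power for these outcomes. Its only sample size is for time in range: difference 5, SD 9, two-sided 5% level, 80% power. The t-based solution is 51.84 per arm, so 52 per arm and 104 in total, as stated. I use 52 per arm below only as a scale.

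**General result.** Let baseline SD be s0, follow-up SD s1 and correlation rho. Per participant:

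- change score: s0² + s1² − 2·rho·s0·s1
- ANCOVA: s1²·(1 − rho²)
- difference: (s0 − rho·s1)², which is never negative

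Apart from the one degree of freedom spent, ANCOVA is therefore at least as precise, whether or not the variances are equal.

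**Equal variances.** The ratio is 2(1 − rho)/(1 − rho²) = 2/(1 + rho). The interval is wider by the square root of the ratio, minus 1. The effective number out of 104 is 104 divided by the ratio. The last column is the power under change scores for an effect that ANCOVA would detect with 80% power: Φ(2.80/√ratio − 1.96).

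| rho (assumed) | Variance ratio | Interval wider by | Effective number of 104 | Power |
|---|---|---|---|---|
| 0.5 | 2/1.5 = 1.33 | 15.5% | 78 | 68% |
| 0.7 | 2/1.7 = 1.18 | 8.5% | 88 | 73% |
| 0.9 | 2/1.9 = 1.05 | 2.6% | 99 | 78% |
| 0.95 | 2/1.95 = 1.03 | 1.3% | 101 | 79% |

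The power column is illustrative, since the SAP claims no power here. The ANCOVA degree of freedom costs about 1% of variance at 52 per arm, which takes 1.33 to 1.32 at rho 0.5.

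**Chance imbalance.** If the arms differ at baseline by D (in SD units), the change-score estimate shifts by −(1 − rho)·D. One standard error of D at 52 per arm is √(2/52) = 0.196. For D = 0.2 the shift is 0.10 SD at rho 0.5, 0.06 at 0.7 and 0.02 at 0.9.

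This is not a second loss. The variance of (1 − rho)·D is (1 − rho)²·2/n. The excess variance of the change score is (2/n)·[2(1 − rho) − (1 − rho²)] = (2/n)·(1 − rho)². The two are identical; at rho 0.5 and n = 52 both equal 0.0096.

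**Simulation** (20,000 trials, 52 per arm). At rho 0.5, 0.8 and 0.95 the variance ratios were 1.31, 1.10 and 1.02. The mean error over all trials was about 0 for both methods. In trials with an imbalance of 0.15 to 0.25 SD, the change-score estimate was off by −0.094, −0.039 and −0.007 SD, and ANCOVA by about 0.

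**The case against.** The strongest defence is that these outcomes are exploratory, are defined as changes, and an unadjusted comparison of change is a valid pre-specified analysis of them. Effectiveness is judged on the primary outcome, which is baseline-adjusted. That stands, and it limits the importance of the point. It gives no reason to prefer the less precise model when the covariate is already collected.

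Four stronger readings are tempting, and the SAP does not support them.

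- **The estimate is biased.** Under 1:1 random allocation the change-score estimator is unbiased over randomisations. The shift for a given imbalance is the same efficiency loss seen conditionally, and the change-score interval already allows for it.
- **All other continuous outcomes are adjusted.** Fasting capillary glucose has a mixed model with arm as the only fixed effect named, and the rank-sum fallback for the glucose outcomes expressly drops baseline adjustment.
- **Imbalance in the subtracted value is hidden.** The baseline table does list "Total daily insulin (units) at enrolment", and basal proportion at enrolment, before at least five weeks of run-in. For these two the subtracted value is not shown. Weight, however, is listed at randomisation.
- **The logarithmic fallback cannot work.** It could if the positive raw values were logged before differencing. The SAP does not say so, which makes it an ambiguity to settle.

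It is also fair to say that the size is unknown, because no rho is given and the equal-variance formula is an assumption.

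**Conclusion.** The point holds as one of efficiency and consistency. The clinical-outcome model omits a baseline value that the SAP has available and uses for the primary outcome and most other continuous secondary outcomes.

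Under equal variances, the loss ranges from modest (variance up by a third at rho 0.5) to trivial (about 3% at 0.95). It could matter for insulin dose, basal share and carbohydrate ratio. For weight it would be negligible if the correlation is high, as one would expect. That the loss cannot be negative, apart from the one degree of freedom, needs no assumption about rho or equal variances; its size does.

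Type I error and the average validity of the intervals are not in question, and the primary conclusion is unaffected.

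**What to change.** Replace the model sentence under Clinical outcomes with wording such as: *Each clinical outcome at mid-study and at end-of-study will be analysed by ANCOVA with treatment arm and the value at randomisation as covariate; the same covariate will be included in the regimen interaction models.*

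Change can remain the reported quantity. If change = a + b·arm + c·baseline, then follow-up = a + b·arm + (c + 1)·baseline, so the arm coefficient b is the same either way.

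Add that any logarithm is taken of the positive follow-up and randomisation values, not of the change.

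Optionally, show total daily insulin and basal proportion in the baseline table at randomisation as well as at enrolment.

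The cost is one sentence, a clause on the logarithm, two optional table rows and one degree of freedom per model. No new data are needed.

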Secondary

To determine the effectiveness of 6 months closed-loop compared with manually determined insulin dosing on glucose control, psychosocial well-being, sleep, cognitive functioning, ECG and health economics measures in adults with type 1 diabetes.

Section 3: Study Methods

Trial design

HCL-Adult is a multicentre, open label, parallel-group, superiority randomized clinical trial with equally sized treatment groups.

The intervention will last for 26 weeks, with an additional minimum 5 week period of active run-in which includes education (pre-randomisation). The exact duration of run-in will depend on individual training requirements. The study flow is presented in Figure 1.

Randomization

Group allocation (HCL or continuing standard care) will be random with a 1:1 ratio using minimization with 3 stratification variables, all of which are expected to be highly prognostic of primary outcome. These minimization variables are: 1) % time in target range pre-randomisation (dichotomised into <= 55% and > 55%); 2) study centre (7 sites); and 3) insulin delivery modality at enrolment (MDI or IPT). Due to the nature of the intervention, blinding of participants and investigators is not possible.

Sample size

Sample size calculation is based on a parallel design with 2 equally sized groups.

Assumptions used were derived from JDRF CGM randomized clinical trials [8, 9] that recruited a sample of 69 adults (25-70 years old) with type 1 diabetes and a baseline HbA1C < 10.5%, 86% of whom were using IPT and 14% using MDI. All participants had masked CGM data at randomization and at 6 months. Study investigator [name], personal communication, provided estimates of the effective standard deviation of percentage time spent in target glycaemic range at 6 months (adjusted for baseline) which was 9% (95% CI 8% to 12%) for pump users and 10% (95% CI 7% to 19%) for MDI users.

To detect a difference in percentage time in target glycaemic range of 5% with 80% power and 5% type I error rate assuming a common standard deviation of 9%, a total of 104 participants are needed. Allowing a drop-out rate of 10% a total of 120 people will be recruited, 60 randomized to HCL while 60 randomized to control group.

A more conservative scenario with a dropout rate of 20%, and unequal SDs of 12% and 19% for IPT and MDI users, respectively, increases the minimum detectable absolute difference to 9% with a power of 80%.

Framework

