This study is a superiority study with all analysis being performed on this basis.

Statistical interim analyses and stopping guidance

No interim analysis is planned. The study device has been previously proven to be safe for people with type 1 diabetes [10]; therefore, early stopping due to safety issues is not expected. However, safety recommendations will be made by an independent Data Safety Monitoring Committee (DSMC).

Timing of final analysis

The primary outcome and secondary glucose outcomes will be analysed collectively at the conclusion of the study. Other secondary outcomes will be analysed separately at the end of the study.

Health economic outcome and biomarkers will be analysed at a later date after additional funding is obtained.

Timing of outcome assessments

Pre-randomisation outcomes are collected at Visits 3-6, mid-study outcomes are collected at Visits 9-11 and end-of-study outcomes are collected at Visits 12-15 (Figure 1)

[figure not shown]

Figure 1: Study flow and timing of outcome assessments

Section 4: Statistical principles

Confidence intervals and p values

All hypothesis testing will be two-sided with an α of 0.05, with reported 95% confidence intervals.

No corrections for multiplicity are planned to control Type I error; rather, the effectiveness of the intervention will be assessed based on the clearly specified primary outcome; secondary outcomes are exploratory in nature and will be labelled as such in publications arising from the study. A transparent approach to reporting results will be taken, with the list of all pre-specified secondary outcomes included in every publication resulting from this study (this list would include a reference to relevant publication if results already published).

Results will be interpreted in light of the number of comparisons and where multiple comparisons indicate multiple effects, the consistency of these results will be discussed.

Adherence and protocol deviation

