Section 6 Analysis

Primary outcome

Outcome definition

Primary outcome is the percentage of time spent in target glucose range (3.9-10 mmol/L) measured by masked CGM over 3 weeks starting at 23 weeks post randomization (\pm 3 weeks) (glucose measured at 5-min intervals). Participants with a low number of available CGM readings in one or more weeks will have the CGM repeated and may have up to 5 weeks of masked CGM collection. To accurately represent participant's glycaemic status, only days with at least 70% valid CGM readings will be used (>= 202 valid readings) [11]. The percentage of time spent in target glucose range will be calculated by dividing the number of sensor readings falling in the range 3.9 – 10 mmol/L by the total number of sensor readings and multiplying by 100 over the whole period of masked CGM collection. If the participant has less than 10 representative days [11] their outcome will be counted as missing (individual glucose values will not be imputed).

Analysis methods

To test for an effect of the treatment group on the primary outcome, an ANCOVA including treatment arm and baseline percent time in target range will be conducted. The primary outcome will be analysed on an intention-to-treat basis on the entire study population with missing outcome data imputed using multiple imputations under missing at random (MAR) assumption (overall time in range will be imputed rather than single glucose values, see section on Missing data).

Results will be presented as the mean difference in the percent time in target range between treatment arms at the end of the study with 95% confidence interval and p value.

Model residuals will be visually inspected to test the assumptions of the model. In the event of violations to homoscedasticity and non-normal distribution, the outcome will be transformed using a natural logarithm. If the ANCOVA model still displays poor fit, non-parametric analysis (Wilcoxon rank sum test) will be employed.

Sensitivity analyses

- 1. ANCOVA with adjustment for factors used in the minimisation will be conducted (study centre 7 categories, insulin delivery modality 2 categories).
- 2. Replication of primary outcome analysis in complete case population (missing completely at random (MCAR) assumption)
- 3. Replication of primary outcome analysis in full study sample using multiple imputation of missing data under missing not at random (MNAR) assumption (see section Missing data)

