- 4. Replication of primary outcome analysis in per-protocol population (see population definitions).

Planned subgroup/interaction analyses

The differential effect of the intervention on the primary outcome based on insulin regimen at enrolment (IPT or MDI) will be examined using a linear regression including terms for treatment group, regimen, a treatment group by regimen interaction, and baseline time in range.

Missing data

See Missing data section below.

Secondary outcomes

1. Glucose control

Outcome definition

Percent time in ranges (day/night/overall)

Percent time spent in the following ranges will be examined.

- 3.9 10.0 mmol/L
- < 2.8 mmol/L

- < 3.0 mmol/L*

- < 3.3 mmol/L

- < 3.9 mmol/L

- 3.9 7.8 mmol/L
- > 10.0 mmol/L
- > 13.9 mmol/L
- > 16.7 mmol/L

Percentage of time spent in each glucose range will be calculated by dividing the number of sensor readings falling in the range by the total number of valid sensor readings and multiplying by 100. This will be performed separately for day (6:00-23:59), night (00:00-5:59) and overall. Values will be calculated at baseline, mid-study, and end-of-study using masked CGM collection.

- Mean glucose level, standard deviation and coefficient of variation (SD/mean)

These metrics will be calculated using valid readings only, separately for day (6:00 - 23:59), night (00:00 - 5:59) and overall. Values will be calculated at baseline, mid-study, and end-of-study using masked CGM collection.

Fasting capillary blood glucose

Fasting capillary blood glucose is defined as the first capillary blood glucose taken between 5 am and 9 am during the period of masked CGM collection. These are recorded separately in blood glucose meters.

- HbA1c

HbA1c is measured from blood sample at enrolment, randomisation, mid-study (3 months post randomisation) and end-of-study (6 months post randomisation).

- 1.5-anhydrogluticol

This biomarker is measured at randomisation and end-of-study.

^{*}This outcome was not part of initial protocol, however it was added due to the position statement of the American Diabetes Association and the European Association for the Study of Diabetes published in 2017 ([12])

- Hypoglycaemic events

Events of symptomatic hypoglycaemia are defined as episodes of hypoglycaemia with glucose level < 3.5 mmol/L confirmed by a finger prick and requiring carbohydrate rescue. These events are self-reported and collected in participant's diary throughout the study.

Analysis method

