- Severe hypoglycaemia, defined as hypoglycaemia requiring the assistance of another person to actively administer carbohydrate, glucagon, or take other corrective actions (n)
- Infections and inflammation at sensor and insulin delivery line insertion sites

Analysis method

Safety outcomes will be presented as a count of events for each treatment group and percentage of participants experiencing at least one event in each treatment group. No formal statistical tests will be performed.

Sensitivity analysis

Due to exploratory nature of the outcomes, no sensitivity analysis will be performed.

Subgroup analysis

Separate analysis for each regimen will be performed.

Missing data

Baseline variables are expected to have minimal missing data. Missing data in outcome variables are more likely to be arbitrary missing than monotone missing, therefore missing data will be multiply imputed using a multivariate normal regression imputation method given smaller sample size [14]. All the imputations will be performed separately for each treatment arm [15]. Baseline and midstudy variables will be considered to be included in the model based on their correlation with the outcome. The number of imputations will be contingent upon the missing proportion: if $\leq 30\%$ missing, 20 imputations will be generated; if >30% missing, 40 imputations will be generated [16].

In the event of violations to regression assumptions, hence non-parametric methods are required, simple imputation will be performed, replacing the missing value with the median of the treatment arm.

Secondly delta-adjusted multiple imputations will be conducted under the missing not at random (MNAR) assumption using the following deltas: -1SD, +1SD.

If unexpected patterns of missing data are found, additional post-hoc sensitivity analysis will be performed.

Additional analyses

1. Missing data patterns

The patterns of missing data overall and within masked CGM will be explored, in particular time of the day and day of the week. Further analysis might be performed based on initial results.

- 2. Study process measures
 - a. Time from enrolment to randomisation (days)
 - b. Days between randomisation and end-of-study visit
- c. Amount and percent time valid sensor readings during masked CGM periods Median, interquartile range, minimum and maximum values will be presented overall and separately for each treatment group.

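### The imputation of the primary outcome names no end-of-study variable, so a short final CGM record and 6-month HbA1c are left out; the gain from adding them is modest

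*SAP*

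**What the plan says.** The outcome definition (SAP Section 6, Primary outcome) counts only days with at least 70% valid readings and then states: "If the participant has less than 10 representative days [11] their outcome will be counted as missing". A participant with too few readings has CGM repeated, for up to 5 weeks of collection. The primary analysis imputes overall time in range under missing at random.

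The Missing data section specifies multivariate normal regression imputation, run separately by arm. On predictors it says only: "Baseline and midstudy variables will be considered to be included in the model based on their correlation with the outcome". It adds delta-adjusted imputation at -1SD and +1SD as a missing-not-at-random sensitivity analysis.

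End-of-study data other than the primary outcome are collected. Under Secondary outcomes, Glucose control: "HbA1c is measured from blood sample at enrolment, randomisation, mid-study (3 months post randomisation) and end-of-study (6 months post randomisation").

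No planned analysis of the primary outcome is stated to use either the short record or the 6-month HbA1c:
- The complete-case analysis omits these participants.
- The delta analysis shifts imputed values.
- The non-parametric fallback inserts the arm median.

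**The concern.** The primary outcome can be missing because a participant left before the final window, or because the participant was present but produced too few valid days. In the second case the trial holds 1 to 9 days of the very quantity being imputed and, if the final blood sample was taken, a 6-month HbA1c. As written, someone with 9 valid days is imputed like someone who left after mid-study.

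Two things are at stake. One is precision, because concurrent data should predict the missing value better than 3-month data do. The other is how credible missing at random is. If short records go with worse glycaemia at 6 months, conditioning on earlier data alone will not fully account for that.

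**Working it through.** **Reproducing the plan's figure.** Input from SAP Section 3, Sample size: "To detect a difference in percentage time in target glycaemic range of 5% with 80% power and 5% type I error rate". The same section takes the SD, adjusted for baseline, as 9 percentage points in both groups. From Section 4: "All hypothesis testing will be two-sided with an α of 0.05".
- Normal approximation: 2 × (1.960 + 0.842)² × 9² / 5² = 50.9, so 51 per arm (102 in total).
- Two-sample t calculation: 52 per arm, matching "a total of 104 participants are needed".
- 104 / 0.90 = 115.6, so 116. The SAP recruits 120 ("Allowing a drop-out rate of 10% a total of 120 people will be recruited"), which is slightly generous.

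**Assumptions not in the SAP.**
- Share with 1 to 9 valid days, f: 3%, 5% or 10%. The SAP's 10% and 20% are dropout rates, a different quantity.
- Baseline-adjusted correlation with the outcome: 0.4 or 0.6, for mid-study time in range and for end-of-study HbA1c.
- Day-to-day SD of time in range, s: 12, 18 or 24 points.
- Valid days in the short record, k: 2, 5 or 9. A full record is 21 days.

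**Strength of the imputation model.** Taking the predictors as independent given the outcome,
1/(1 − R²) = 1 + Σ r²/(1 − r²) + 81 / [s²(1/k − 1/21)],
where the last term applies only when the short record is used.
- Mid-study only: R² = 0.16 to 0.36.
- Adding HbA1c: 0.28 to 0.53.
- Adding HbA1c and the short record: 0.41 to 0.91.

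**Precision.** The variance of an arm mean, relative to complete data, is R² + (1 − R²)/(1 − f).

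| f | R², plan → fix | Factor, plan | Factor, fix | SE ratio |
|---|---|---|---|---|
| 5% | 0.36 → 0.52 | 1.0337 | 1.0253 | 1.004 |
| 5% | 0.16 → 0.91 | 1.0442 | 1.0047 | 1.019 |
| 10% | 0.36 → 0.52 | 1.0711 | 1.0533 | 1.008 |
| 10% | 0.16 → 0.91 | 1.0933 | 1.0100 | 1.040 |

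These rows are the extremes of the grid. At f = 3% the excess is 0.2 to 1.1%.

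**Power for 5 points**, with effective N = 120 / factor and no other loss:
- 5% affected: 84.6 to 84.9% under the plan, 85.0 to 85.9% with the fix.
- 10% affected: 82.9 to 83.7% under the plan, 83.8 to 85.7% with the fix.

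The gain is about 0.3 to 2.8 points. Dropout would lower both sets of figures, so the levels are not a forecast.

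**Bias.** Large-sample regression imputation by arm (400,000 per arm), correlations 0.5, s = 18, short records of 1 to 9 days, all available days used. Bias is about zero when short records are random, depend on mid-study status, or depend on end-of-study glycaemia equally in both arms. When the chance of a short record doubles per SD of worse end-of-study glycaemia in one arm only:

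| f | Plan | + HbA1c | + HbA1c and short record |
|---|---|---|---|
| 3% | 0.12 | 0.09 | 0.05 |
| 5% | 0.21 | 0.16 | 0.09 |
| 10% | 0.44 | 0.34 | 0.18 |

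HbA1c alone removes about a quarter of the bias (0.44 to 0.34 is 23%). With the whole short record added, more than half goes (0.44 to 0.18 is 59%).

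**The case against.** A reader might infer four stronger things that the document does not support.

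1. **That end-of-study predictors are excluded.** The SAP says which variables will be considered and rules out no others. A multivariate normal model can carry several incomplete variables, so an analyst could add them. This stands. Even so, it leaves open whether 6-month data enter the primary imputation, and a pre-specified plan should settle that.
2. **That the data are thrown away.** HbA1c is a planned secondary outcome, and the secondary CGM metrics do not repeat the 10-day rule. What is missing is a role for these data in imputing the primary outcome.
3. **That the primary estimate is biased.** Nothing in the SAP shows that short records depend on 6-month glycaemia, still less differently by arm. The outcome comes from masked CGM, so low wear of the study sensor is not the same as poor engagement with the closed-loop device. The delta analysis also probes such departures: with an SD of 9 and 10% missing in one arm, a 1SD shift moves that arm's mean by 0.9 points, more than the 0.44 above. This stands, except that the delta analysis uses none of the observed end-of-study values and does not alter the primary estimate.
4. **That most of the lost precision would come back.** The share recovered is (R² fix − R² plan)/(1 − R² plan). It runs from (0.52 − 0.36)/0.64 = 25% to (0.91 − 0.16)/0.84 = 89%, depending wholly on assumed correlations and days.

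Repeat CGM for up to 5 weeks should also keep the affected group small.

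**Conclusion.** The point holds as a modest improvement to the primary imputation model. The plan names no end-of-study predictor, although relevant end-of-study data may be in hand for participants who fall short of 10 days. The avoidable loss is an SE 0.4 to 1.9% larger if 5% are affected and at most about 4% larger if 10% are. Power remains above 80% when short records are the only loss. Bias is a possibility and has not been demonstrated: about 0.1 to 0.4 points at 3 to 10% affected, and only if short records depend on end-of-study glycaemia differently by arm.

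All of these sizes rest on assumed correlations, day-to-day variation and, above all, an assumed share of short records. The bias reduction of more than half is for a model that uses every available day. A summary based on a fixed number of days should fall between that and the HbA1c-only figures.

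**What to change.** Extend the predictor sentence in the Missing data section so that the multivariate normal model for the primary outcome, run within each arm, also includes:
- end-of-study HbA1c; and
- time in range from a fixed small number of valid end-of-study days, with the number stated in advance. Compute it the same way for every participant and treat it as missing where fewer days exist.

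Fixing the number of days matters. Otherwise a one-day mean and a nine-day mean enter one normal model with very different error. Keep the 10-day rule for the outcome itself.

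The cost is SAP wording and two more columns in the imputation model, with no new data and no burden on participants. The downsides are a slightly larger model with about 60 participants per arm, and that participants with fewer than the stated number of days gain only from HbA1c.
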